#### **Molecular aspects:**

- Assessment of AR-V7 mutation prior to the start of study treatment and at time to documented progression disease or treatment end.
- Determination changes in CTCs number prior to the start of study treatment and at time to documented progression disease or treatment end.
- The molecular analysis will be conducted on the modified full analysis set.

#### **Methods for secondary efficacy analysis and molecular aspects.**

The PFS, OS, time to first symptomatic SSE, rPFS and alkaline phosphatase level response (AF) will be described with Kaplan-Meier method. Number and proportion of events and median survival time, with corresponding 95% CI, will be calculated. We will describe the number and percentage of patients with AR-V7 mutation and CTCs at the start and at the end of the study. The evolution of these measures in the study will be analyzed with Mc Nemar's test. The 95% confidence interval for the difference of proportions will be based on the Wald with Bonett-Price Laplace adjustment. All tests were will be one-sided, and P values of 0.025 or less were considered to indicate statistical significance. If there are very few AR-V7 patients recruited, outcomes will be only described.

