Radium-223 (Xofigo[®]) is indicated for the treatment of patients with mCRPC with symptomatic bone metastases and no known visceral metastatic disease. In the pivotal phase III clinical trial (the ALSYMPCA study), a total of 921 subjects with mCRPC with bone metastases were randomly assigned, in a 2:1 ratio, to receive six injections of radium-223 (at a dose of 50 kBq per kilogram of body weight intravenously) or matching placebo; one injection was administered every four weeks[16]. Prior to randomization, 58% and 57% of patients had received docetaxel in the radium-223 and placebo arms, respectively. The median duration of treatment was 20 weeks (six cycles) for radium-223 and 18 weeks (five cycles) for placebo. Radium-223, as compared with placebo, significantly improved OS (median, 14.0 vs. 11.2 months; HR, 0.70; 95% CI, 0.55 to 0.88; P=0.002). The updated analysis involving 921 patients confirmed the radium-223 survival benefit (median, 14.9 vs. 11.3 months; HR, 0.70; 95% CI, 0.58 to 0.83; P<0.001). Assessments of all main secondary efficacy endpoints also showed a benefit of radium-223 as compared with placebo. The most common AEs ($\geq 10\%$) in patients receiving radium-223 were nausea (2% grade 3-4), diarrhea (2% grade 3-4), vomiting (2% grade 3-4), and peripheral edema (2% grade 3-4). The most common hematologic laboratory abnormalities in radium-223-treated patients ($\geq 10\%$) were anemia (6% grade 3-4), lymphocytopenia (20% grade 3-4), leukopenia (3% grade 3-4), thrombocytopenia (3% grade 3-4), and neutropenia (2% grade 3-4). Treatment discontinuations due to AEs occurred in 17% of patients who received radium-223 and 21% of patients who received placebo.

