8.4. Efficacy results

Primary endpoint

We will analyze PFS in both cohorts with one arm Log-Rank test. This time endpoint will be described with Kaplan-Meier method. We will calculate number and proportion of events and median survival time, with corresponding 95% CI.

Secondary endpoints

We will describe the number and percentage of patients with AR-V7 mutation and CTCs at the start and at the end of the study. The evolution of these measures in the study will be analyzed with McNemar's test and paired odds ratio (OR) with corresponding 95% CI.

OS, time to first symptomatic SSE, rPFS and alkaline phosphatase level response (AF) will be described with Kaplan-Meier method. Number and proportion of events and median survival time, with corresponding 95% CI, will be calculated.

Subgroup analysis

The AR-V7-negative and positive cohorts at baseline will be compared for all analysis. For timed endpoints (PFS, OS, time to first symptomatic SSE, TTP-AF, and TTP-PSA), we will use the Kaplan-Meier method and Log-Rank test. For binary outcomes we will use chi-squared or Fisher's exact tests.

Levels of CTCs at the start and at the end of the study will be correlated with timed and binary endpoints. For timed and binary endpoints we will use Cox analysis and logistic regression, respectively.

We also analyse PFS and OS with multivariable Cox proportional hazards models for adjusting for AR-V7 status, CTCs levels and relevant baseline covariates, including Gleason score, PSA level, number of prior hormonal treatments, the presence or absence of visceral metastases, the Eastern Cooperative Oncology Group (ECOG) score, prior use of abiraterone acetate or enzalutamide, and the level of full-length (FL) androgen receptor. All tests were two-sided, and P values of 0.05 or less were considered to indicate statistical significance. We will examine the residuals to assess model assumptions and only first-order interactions will be evaluated. We will calculate relative risk (RR) and HR with corresponding 95% CI to compare dichotomous and time to event variables, respectively. Up-to-date versions of R will be used to conduct analyses.

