### 7.2.1 Summary statistics

#### Efficacy:

- OS is defined as the time from inclusion until death from any cause or the last date the patient was known to be alive. Patients who are lost to follow-up and the patients who are alive at the date of data cut-off are censored at the date the patient was last known alive (censoring rules are specified in
  - Appendix I). The OS will be assessed by cohorts.
- Time to first SSE is defined as the time from treatment initiation until SSE (pathological fractures, vertebral or non-vertebral, spinal cord compression, radiation or surgery to bone). For all other events, the start date of the event/medication/therapy was used as the time of the event. If an event has not occurred at the time of the analysis or the patient has been lost to follow-up, the time-to-event variables will be censored at the last disease assessment date.
- The time from the first study drug administration to when PSA progression was observed, defined as:
  - 1) In subjects with no PSA decline from baseline:  
a greater than or equal to 25% increase from baseline value and an increase in absolute value of greater than or equal to 2 ng/mL, at least 12 weeks from baseline;
  - 2) In subjects with initial PSA decline from baseline:

the time from start of treatment to first PSA increase that is greater than or equal to 25% increase and at least 2 ng/mL above the nadir value, which was confirmed by a second value obtained three or more weeks later.

- Determination percentage of PSA progression (defined as PSA elevation  $\geq 25\%$  and  $\geq 2$  ng/mL after 12 weeks).
- Alkaline phosphatase (AF) level response, normalization of alkaline phosphatase level (progression defined as AF elevation  $\geq 25\%$  after 12 weeks). The patients will be classified according on whether there is AF progression or not.
- Radiographic progression-free survival (rPFS) depending on AR-V7 status.

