#### **7.2.2 Subgroup Analysis**

The AR-V7-negative and positive cohorts at baseline will be compared for all analysis. All subgroup analysis will be based on the full analysis and per protocol sets. If there are very few AR-V7 patients recruited, outcomes will be only described.

For time to event endpoints (PFS, OS, time to first symptomatic SSE, TTP-AF, and TTP-PSA), we will use the Kaplan-Meier method and Log-Rank test. For binary outcomes we will use Chi-squared or Fisher's exact tests.

We also analyze PFS and OS with multivariable Cox proportional hazards models including AR-V7 status, CTCs levels and other relevant baseline covariates, including PSA level, number of prior hormonal treatments, the presence or absence of visceral metastases, the Eastern Cooperative Oncology Group (ECOG) score, and prior use of abiraterone acetate or enzalutamide. All tests were two-sided, and P values of 0.05 or less were considered to indicate statistical significance. We will examine the residuals to assess model assumptions and only first-order interactions will be evaluated. We will calculate relative risk (RR) and HR with corresponding 95% CI to compare dichotomous and time to event variables, respectively.

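### Time to first symptomatic skeletal event is described by Kaplan-Meier with no provision for death as a competing event, so the curve and median overstate the real-world risk

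*SAP*

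**What the plan says.** Time to first SSE is a secondary efficacy endpoint. SAP 7.2.1 reads "Time to first SSE is defined as the time from treatment initiation until SSE (pathological fractures, vertebral or non-vertebral, spinal cord compression", and goes on to radiation or surgery to bone. Protocol 8.3.2 uses the same definition. Death is not part of the event.

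The censoring rule is general. It applies "If an event has not occurred at the time of the analysis or the patient has been lost to follow-up", and then "the time-to-event variables will be censored at the last disease assessment date". Death is not named in it.

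The analysis is Kaplan-Meier in both documents: protocol 8.4 has "OS, time to first symptomatic SSE, rPFS and alkaline phosphatase level response (AF) will be described with Kaplan-Meier method", and the methods paragraph of SAP 7.2.1 likewise has "time to first symptomatic SSE, rPFS and alkaline phosphatase level response (AF) will be described with Kaplan-Meier method". The summaries are given as "Number and proportion of events and median survival time, with corresponding 95% CI, will be calculated". For the AR-V7 cohorts, SAP 7.2.2 states "For time to event endpoints (PFS, OS, time to first symptomatic SSE, TTP-AF, and TTP-PSA), we will use the Kaplan-Meier method and Log-Rank test".

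Neither document mentions cumulative incidence, any other competing-risk method, or SSE-free survival. Protocol 8.6 defends the censoring of withdrawals on the condition that dropout is unrelated to prognosis. It does not discuss death for an endpoint that excludes death.

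**The concern.** A man who dies without an SSE fits only the general rule, so he is censored. Kaplan-Meier then assigns him the later SSE risk of the men still alive, although he can no longer have an SSE. The complement of the curve (1−KM) estimates SSE risk in a setting without death, not the share of patients who will have an SSE. Exact censoring dates do not cure this.

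In a single-arm trial with no comparator, readers will take the curve and the median as absolute statements about skeletal risk after radium-223. If deaths are frequent, both will look worse than what patients experience.

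**Working it through.** **Plan's own figure.** There is none to reproduce. The documents give no expected SSE rate, SSE median or precision target. The check therefore uses the survival and follow-up figures that they do give, with a range of assumed SSE rates.

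**Inputs**
- Median overall survival (OS) 14.9 months: radium-223 arm of the pivotal trial, protocol 1.2, "median, 14.9 vs. 11.3 months".
- Median OS 32.4 months: enzalutamide arm of the trial in men without prior docetaxel, protocol 1.1.
- Uniform accrual over 23 months plus 11 months of follow-up, maximum 34: protocol 8.2.
- Assumed: SSE median (ignoring death) of 12, 24 or 36 months; constant, independent hazards λs for SSE and λd for death, each ln 2 / median.

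**Step 1: is death common by the efficacy cut-off?**
Share dead = 1 − [exp(−11λd) − exp(−34λd)] / (23λd).
- OS 14.9: λd = 0.04652; 1 − (0.5995 − 0.2056)/1.0700 = 63%.
- OS 32.4: λd = 0.02139; 1 − (0.7903 − 0.4832)/0.4920 = 38%.

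**Step 2: 24-month risk on the two scales.**
1−KM = 1 − exp(−λs·t). Cumulative incidence = λs/(λs+λd) × [1 − exp(−(λs+λd)·t)].
With SSE median 24, λs = 0.02888 and 1−KM = 50.0%.
- OS 14.9: 0.3830 × (1 − exp(−1.8096)) = 0.3830 × 0.8363 = 32.0%.
- OS 32.4: 0.5745 × (1 − exp(−1.2066)) = 0.5745 × 0.7008 = 40.3%.

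| Assumed SSE median (months) | 1−KM at 24 months | Cumulative incidence, OS 14.9 | Cumulative incidence, OS 32.4 | Excess (points) |
|---|---|---|---|---|
| 12 | 75.0% | 50.9% | 62.1% | 12.9 to 24.1 |
| 24 | 50.0% | 32.0% | 40.3% | 9.7 to 18.0 |
| 36 | 37.0% | 23.2% | 29.5% | 7.5 to 13.8 |

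Over the same grid the excess is 2 to 11 points at 12 months and 13 to 32 points at 34 months.

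**Step 3: the median, which the plan does list.** Take a Kaplan-Meier median of 24 months.
- OS 14.9: cumulative incidence levels off at λs/(λs+λd) = 38.3%, so half of the patients never have an SSE.
- OS 32.4: 50% is reached at −ln(1 − 0.5/0.5745)/0.05027 = 40.6 months.

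**Step 4: simulation check.** With 200,000 patients per scenario, cut-off uniform between 11 and 34 months and SSE median 24, 24-month 1−KM was 50.2% and 49.8% against a cumulative incidence of 32.1% and 40.2% (OS 14.9 and 32.4). The crude share of patients with an observed SSE was 30.5% and 37.7%, which does not carry the inflation.

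**Step 5: direction.** In any data set 1−KM is at least as large as the Aalen-Johansen estimate, and larger once an SSE-free death precedes a later SSE. The size depends on the assumed rates; the direction does not.

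**Step 6: the censoring date, which the fix must settle.** Protocol Appendix 1 (note 12) ends scheduled imaging at progression, while SSEs are still followed afterwards (protocol 3.2 and 5.3). Suppose that the last disease assessment means the last scan, that later SSEs still count, and that median progression is 6.3 months (the design target), with SSE median 24. Simulated 24-month 1−KM then becomes 84.6% (OS 14.9) and 82.3% (OS 32.4), against 32.1% and 40.2%. Under that reading most men who die would leave the risk set before their death could count as a competing event.

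**The case against.** Several points on the other side stand.

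- **Listed summaries.** No landmark 1−KM percentage is planned. A reader might infer that the reported proportion of SSEs will be inflated. It will not: it is a crude count over the number of patients. Of the listed summaries only the median and its interval are affected, together with the curve itself.
- **Cohort comparison.** A reader might infer that a mortality difference between AR-V7 cohorts would bias the comparison. The log-rank test compares cause-specific SSE hazards, for which removing SSE-free deaths from the risk set is standard. Only the gap between the curves, read as a difference in risk, misleads. SAP 7.2.1 and 7.2.2 also allow description only if few AR-V7-positive men are recruited.
- **Extension.** A reader might infer that the 2-year extension analysis is affected. SAP 7.2 and protocol 8.3.2 end every efficacy endpoint except OS at 34 months, and no Kaplan-Meier analysis of skeletal events is specified for the extension.
- **Wording.** Censoring at death is implied by the general rule, not written.
- **Survival anchor.** The 14.9 months comes from a trial in which 58% of the radium-223 arm had prior docetaxel. This trial requires asymptomatic men, no visceral metastases and a life expectancy of at least 12 months. That argues for longer survival, which is why the 32.4-month anchor is shown. Yet that anchor comes from a trial of enzalutamide itself, whereas these men have already progressed on abiraterone or enzalutamide, so it may be generous.
- **Precision.** With 52 patients a binomial 95% half-width is about 12 points at 30% (1.96 × √(0.21/52)) and 14 at 50% (1.96 × √(0.25/52)), similar to the excess. But the excess is systematic, and the Kaplan-Meier interval would not reflect it.

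Kaplan-Meier is legitimate here if it is labelled as a cause-specific description. The plan neither labels it nor offers an absolute-risk estimate beside it.

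**Conclusion.** The concern holds for the Kaplan-Meier curve and the median time to first SSE. Both overstate the real-world risk because SSE-free deaths are, by implication, censored and no competing-risk estimate is planned. At 24 months a 1−KM of 50% corresponds to about 32% (OS 14.9) to 40% (OS 32.4). A Kaplan-Meier median of 24 months corresponds to half of the patients having an SSE only at about 41 months (OS 32.4), or never (OS 14.9).

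These sizes rest on constant, independent hazards, on assumed SSE rates, and on survival borrowed from two cited trials.

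A reader might go further and infer that the trial's main conclusion is at risk. It is not: the primary PFS composite counts both death and SSE as events (SAP 7.1.1 and Appendix I), and the sample size rests on PFS. This is a worthwhile correction to one secondary endpoint.

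**What to change.** In SAP 7.2.1 and 7.2.2 and protocol 8.4, with the censoring rule in protocol 8.3.2 brought into line:

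1. Report the Aalen-Johansen cumulative incidence of first SSE with 95% CI at 12 and 24 months, overall and by AR-V7 cohort. With 13 AR-V7-positive men expected, that cohort's estimate will be descriptive.
2. State that death without a recorded SSE is a competing event, dated at death.
3. Censor patients alive without an SSE at the last date their SSE status was known, not at the last disease assessment.
4. Keep the Kaplan-Meier curve, labelled as cause-specific, and the log-rank test, for comparability with published results.
5. Add SSE-free survival (SSE or death) by Kaplan-Meier as a companion.
6. If SSE incidence over time is reported for the 2-year safety extension, use the same estimator.

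The cost is SAP and protocol wording and one extra standard analysis in R, which the SAP already specifies. Survival status and SSE follow-up are already collected. The downside is an absolute-risk curve less directly comparable with published Kaplan-Meier SSE curves, which is the reason for showing both.

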##### Molecular aspects:

- Assessment of AR-V7 mutation evolution during the study treatment.
- Determination changes in CTCs number during the study treatment.

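### Change in CTC number is a count endpoint, but the only test and estimates named for it are paired-binary, and no cut-off is stated

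*SAP*

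**What the plan says.** SAP 5.2 (Molecular aspects) lists the endpoint as "Determination changes in CTCs number during the study treatment". SAP 7.2.1 gives its timing: "Determination changes in CTCs number prior to the start of study treatment and at time to documented progression disease or treatment end". Appendix 1 of the protocol schedules a blood sample for a CTC count at screening, end of treatment and progression.

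The methods paragraph of SAP 7.2.1 then treats AR-V7 status and CTCs alike. The summary is: "We will describe the number and percentage of patients with AR-V7 mutation and CTCs at the start and at the end of the study". The test is given next: "The evolution of these measures in the study will be analyzed with" McNemar's test. The estimate is: "The 95% confidence interval for the difference of proportions will be based on the Wald with Bonett-Price Laplace adjustment". The same paragraph sets one-sided testing at 0.025.

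Protocol 8.4 uses the same test with a different effect measure: "The evolution of these measures in the study will be analyzed with McNemar's test and paired odds ratio (OR) with corresponding 95% CI".

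Neither document defines what makes a patient positive for CTCs, and neither names a paired test, estimate or interval for the counts.

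**The concern.** McNemar's test, the difference of paired proportions and the paired odds ratio all reduce each patient to positive or negative at two times. That fits AR-V7 status. It does not fit a change in number, because a patient who is positive at both times is concordant however far the count has moved.

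Two things are at stake. First, the quantity tested is conversion, not the change in number that the endpoint names, so the report could show no change when every count has fallen. Second, the undefined cut-off matters to the result. A fall from 40 to 4 cells is no change if positive means at least 1 cell, and is a change if positive means at least 5. With the cut-off open, it could be chosen after the data are seen.

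**Working it through.** **No figure to reproduce.** The plan gives no effect size, power or sample size for this endpoint. The total of 52 patients was derived from PFS. The number of patients who will have paired CTC samples is not stated; 52 is the ceiling.

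**Step 1: what the test can see.** Let b be the number of patients going from positive to negative and c the number going from negative to positive. Exact McNemar compares b with a Binomial(b + c, 0.5). Counts enter only through b and c.

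Constructed example: 40 patients are positive at both times and every count falls by about 70%. Then b = c = 0 and McNemar p = 1.0. The one-sided signed-rank test on the same counts gives p of about 2 × 10⁻⁸. This step needs no assumption about the trial's data.

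**Step 2: size of the loss, illustrative.** All count parameters are assumptions:
- Baseline count: Poisson, with a patient mean that is lognormal (median 1, 8 or 20; log-SD 1.3).
- Follow-up count: Poisson, with that mean multiplied by an individual fold change (lognormal, median 0.5, log-SD 0.8).
- Tests: exact McNemar and normal-approximation signed-rank, two-sided 0.05.
- 10,000 runs per setting, so the simulation standard error is at most √(0.25/10,000) = 0.5 percentage points.

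Power for a halving of counts:

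| Pairs | Median count | McNemar, cut-off ≥1 | McNemar, cut-off ≥5 | McNemar, cut-off ≥10 | Signed-rank, raw counts | Signed-rank, log(count+1) |
|---|---|---|---|---|---|---|
| 40 | 1 | 27% | 4% | <1% | 46% | 53% |
| 40 | 8 | 19% | 57% | 45% | 88% | 96% |
| 40 | 20 | 2% | 56% | 66% | 94% | 99% |
| 52 | 1 | 38% | 8% | <1% | 58% | 65% |
| 52 | 8 | 30% | 74% | 61% | 95% | 99% |
| 52 | 20 | 5% | 73% | 82% | 98% | >99% |

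Most McNemar entries (13 of 18) lie between about 2% and 71%, against about 48% to 98% for the signed-rank test on raw counts. The corners of the grid run a little wider: below 1% to 82% for McNemar, and 46% at the low end for signed-rank. In every row the signed-rank test is ahead of McNemar at every cut-off.

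**Step 3: a second model.** This uses one-sided 0.025 as in the SAP, mean parameters 2, 5 and 20, between-patient log-SD 1.2, within-patient log-SD 0.6, cut-offs 1 and 5, and 1,500 runs per setting. For a halving with 40 to 52 pairs, McNemar's power was 1% to 68% and signed-rank power was 83% to more than 99%.

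**Step 4: which count analysis.** In the Step 2 model with median fold change 1, the skewed fold changes make raw differences asymmetric. The raw-count signed-rank test then rejects in about 9% to 13% of runs. On log(count+1) it rejects in about 5% to 9%, the upper end arising where counts are very low. The log scale also has the higher power in every row above, so it is the better choice of the two.

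**The case against.** The strongest reply is that counts are not thrown away. Protocol 8.4 correlates CTC levels at start and end with the timed and binary endpoints. SAP 7.2.2 puts CTC levels into the Cox models for PFS and OS. SAP 7.4 lists the baseline CTC count. The general rule in SAP 8.2 summarizes observed values and change from baseline for continuous data collected over time. All of this stands, and a reader who inferred that the trial discards its counts altogether would be wrong. But using a level as a predictor answers a different question from how the level changed, and SAP 8.2 would supply at most a description, with no test, paired estimate or interval for the change.

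A reader might also infer that McNemar's test here registers a change only when a patient crosses zero. Presence or absence is the natural reading of the percentage of patients with CTCs, but no cut-off is given, so zero is an inference. The loss of information holds for any cut-off; its size does not.

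A third tempting reading is a single striking contrast, such as 18% against 88% power with 40 pairs. That figure reproduces for a median count of 8 and a cut-off of 1, but it is one assumed setting. With a cut-off of 5 the McNemar figure is 57%.

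Finally, this is a secondary molecular endpoint in a single-arm phase IIa trial, with no power target or decision rule attached. That limits the consequence and is accepted.

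**Conclusion.** The point holds in this form: the endpoint is change in CTC number, and the only inferential analysis named for it in either document is paired-binary, with no cut-off stated. Changes in count that stay on one side of the cut-off do not enter the test or the estimate of change.

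The mismatch follows from the text and the definition of the test. The size of the loss rests on assumed count distributions, an assumed halving and 40 to 52 complete pairs, and should be quoted as a range. Only the direction was the same in every setting tried. The primary PFS analysis, the AR-V7 analysis and the use of CTC levels as predictors are untouched. It should be corrected because the correction is nearly free, not because the trial's main conclusion is at risk.

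**What to change.** In SAP 7.2.1, with the matching sentence in protocol 8.4:
- Keep McNemar's test and its interval for AR-V7 status.
- For CTC number, name a paired analysis of the counts. One example is the Wilcoxon signed-rank test on log(count+1) differences, with the back-transformed Hodges-Lehmann shift as an approximate fold change and its 95% CI. A count model such as a mixed negative binomial is a reasonable alternative.
- If CTC conversion is also reported, state the cut-off before the paired data are examined.

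The cost is one or two sentences. The counts are already scheduled, so no new samples, visits or patients are needed.

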8.3. Statistical plan

Unless otherwise mentioned all tests will be two-sided.

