### 8.2 *General Methodology*

Definition of baseline: For each safety or efficacy parameter, the last valid assessment made before first study drug administration will be used as the baseline for all analyses of that safety or efficacy parameter unless otherwise specified.

Continuous data will be summarized in terms of the number of observations, mean, standard deviation (STD), median, minimum, maximum, first and third quartiles and NA (not available), unless otherwise stated. Where data are collected over time, both the observed data and change from baseline will be summarized at each time point.

The minimum and maximum will be reported to the same number of decimal places as the raw data recorded in the database. The mean, median and first and third quartiles will be reported to one more decimal place than the raw data recorded in the database. The STD will be reported to two more decimal places than the raw data recorded in the database. In general, the maximum number of decimal places reported shall be four for any summary statistic.

Categorical data will be summarized in terms of the number of subjects providing data at the relevant time point (n), frequency counts and percentages. Changes from baseline in categorical data will be summarized using shift tables where appropriate.

Percentages will be presented to one decimal place. A percentage of 100% will be reported as 100%. Percentages will not be presented for zero counts. Unless otherwise EudraCT number: 2016-001888-36

stated, percentages will be calculated using n as the denominator; for frequency tables not assessed by time point the number of patients considered for every analysis set will be used as denominator. If sample sizes are small, the data displays will show the percentages, but any textual report (e.g. clinical study report) will describe frequencies only.

P-values greater than or equal to 0.001, in general, will be presented to three decimal places. However, if a p-value is only presented to four decimal places it will not be rounded again but will be presented to four decimal places. P-values less than 0.0001 will be presented as “<0.0001”.

Confidence intervals will be presented to one more decimal place than the raw data. A two-sided significance level of 5% will be used for confidence intervals.

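### The SAP makes the McNemar tests of AR-V7 and CTC change one-sided at 0.025 without naming a direction, although the endpoints have none and the protocol's default is two-sided

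*SAP*

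**What the plan says.** SAP 7.2.1, under the methods for secondary efficacy and molecular aspects, describes the time-to-event endpoints with Kaplan-Meier estimates and names one test, for AR-V7 and CTCs: "The evolution of these measures in the study will be analyzed with Mc Nemar's test". It adds an adjusted Wald 95% interval for the difference in proportions and then sets the rule: "All tests were will be one-sided, and P values of 0.025 or less were considered to indicate statistical significance". No direction is stated there or in the endpoint definitions. These read "Assessment of AR-V7 mutation evolution during the study treatment" (SAP 5.2) and "Determination changes in CTCs number prior to the start of study treatment and at time to documented progression disease or treatment end" (SAP 7.2.1).

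Protocol 8.3 sets the default: "Unless otherwise mentioned all tests will be two-sided". Protocol 8.4 plans the same test with no one-sided exception: "The evolution of these measures in the study will be analyzed with McNemar's test and paired odds ratio (OR) with corresponding 95% CI". Later in 8.4, in the subgroup and Cox text, it gives the level: "All tests were two-sided, and P values of 0.05 or less were considered to indicate statistical significance". SAP 7.2.2 repeats that rule for its own subgroup analyses, and SAP 8.2 says of intervals: "A two-sided significance level of 5% will be used for confidence intervals".

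**The concern.** A one-sided test is defined only once its direction is named. The primary analysis does this: it tests whether median PFS is better than a null of 3 months or less. The molecular tests do not. AR-V7 status can be gained or lost and CTCs can rise or fall, and the endpoint wording favours neither.

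As written, someone must choose the direction later, and a change the other way then cannot be declared significant however large it is. The sentence also departs from the protocol's two-sided default without giving a reason. Finally, McNemar's chi-square squares the difference between the discordant counts, so the p-value it gives is two-sided. Comparing that p-value with 0.025 applies a rule that neither document intends.

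**Working it through.** **Inputs.** One-sided 0.025 comes from SAP 7.2.1, two-sided testing from Protocol 8.3, and the 0.05 level from Protocol 8.4. Neither document gives a power, a sample size or an expected number of discordant pairs for these tests, so there is no planned figure to reproduce. All discordant counts below are assumptions.

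**Step 1: the level.** One-sided 0.025 gives z = 1.960. Two-sided 0.05 also gives z = 1.960. In the tested direction the two rules are the same.

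**Step 2: exact McNemar p-values.** With m discordant pairs, of which k go one way, the one-sided p is P(X ≥ k) for X ~ Binomial(m, 0.5), and the two-sided p is twice that. For 10 against 2 (m = 12):

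- tested direction: (66 + 12 + 1)/4096 = 79/4096 = 0.019
- two-sided: 2 × 79/4096 = 0.039
- untested direction: P(X ≥ 2) = 1 − 13/4096 = 0.997

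| Assumed split | One-sided p, tested direction | One-sided p, untested direction | Two-sided p |
|---|---|---|---|
| 6 v 0 | 0.016 | 1.000 | 0.031 |
| 8 v 1 | 0.020 | 0.998 | 0.039 |
| 10 v 2 | 0.019 | 0.997 | 0.039 |
| 12 v 3 | 0.018 | 0.996 | 0.035 |

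All four are significant two-sided at 0.05 and one-sided at 0.025 in the tested direction. None is significant in the untested direction.

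**Step 3: test against interval.** Take 10 against 2 among an assumed N = 40 paired patients. The Bonett-Price interval uses 11/42 and 3/42, so the difference is 8/42 = 0.190. The standard error is √[(14/42 − 0.190²)/42] = 0.084, and the 95% interval is 0.026 to 0.355. If the change runs the untested way, the interval is the mirror image and still excludes zero, while the test reports p = 0.997.

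**Step 4: power.** Take an effect with 80% power at two-sided 0.05, so the standardised effect is 1.960 + 0.842 = 2.802.

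- One-sided 0.025, tested direction: Φ(2.802 − 1.960) = 80%.
- One-sided 0.025, untested direction: Φ(−2.802 − 1.960), about 0.0001%.
- Two-sided p held to 0.025 (z = 2.241): Φ(2.802 − 2.241) = 71.2%. From 90% the fall is to 84.1%.

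Exact power, assuming 80% of discordant pairs go one way:

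| Discordant pairs | Two-sided 0.05 | One-sided 0.025, untested direction | Two-sided p held to 0.025 |
|---|---|---|---|
| 12 | 0.558 | about 0.000005 | 0.275 |
| 20 | 0.804 | about 0 | 0.630 |

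**Step 5: floor.** With 5 pairs all one way, the exact one-sided p is 1/32 = 0.031 and the two-sided p is 0.0625. With 5 or fewer discordant pairs the exact test cannot reach significance under any of these rules.

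**The case against.** The strongest reply is that one-sided 0.025 is the conventional counterpart of two-sided 0.05 and of a 95% interval. On that view the sentence only restates the protocol's level, and the protocol's default leaves room for exceptions. This stands as far as the level goes. A reader might infer that the SAP has halved the significance level, but the text does not support that: in the tested direction all four splits above pass under both rules. The loss of power to 71% arises only if an analyst ignores the word one-sided. It also depends on the version of McNemar's test, which the SAP does not state. The uncorrected chi-square gives p of 0.014 to 0.021 for the four splits, still below 0.025.

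Three other stronger readings also fail.

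- **Frequent reversals.** Between 6 and 20 discordant pairs, an exact two-sided p between 0.025 and 0.05 is possible only at totals of 6, 9, 12, 15, 17, 18 and 20, with one split each.
- **Inflated false-positive error.** Choosing the direction after seeing the data gives about 2 × 0.025 = 0.05 overall, which is the protocol's level.
- **The SAP contradicting itself on the same endpoints.** SAP 7.2.2 concerns cohort comparisons and Cox models, not paired marker status. The protocol's 0.05 sentence likewise sits in its subgroup text. What governs McNemar directly is the two-sided default in Protocol 8.3.

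Reach is also limited. No other test is named in the paragraph, and the SAP falls back to description if very few AR-V7 patients are recruited. That threshold is not quantified; 13 AR-V7-positive patients of 52 are expected.

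None of this supplies the missing direction.

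**Conclusion.** The point holds as a missing direction and an unexplained departure from the protocol's two-sided default. It is not a stricter level. Under a one-sided rule, a real change in the untested direction cannot be significant, even where the accompanying 95% interval excludes zero. The misapplied threshold is a secondary risk that depends on how the p-value is produced.

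The size is minor to moderate. The splits, the 40 paired patients and the 80% share in one direction are illustrative assumptions. Only the AR-V7 and CTC evolution tests are affected. A reader might infer that the trial's declaration of success is exposed, but it rests on PFS in the total sample and is untouched.

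**What to change.** Replace the sentence in SAP 7.2.1 with two-sided tests, significant at P of 0.05 or less. This agrees with the default in Protocol 8.3 and the interval level in SAP 8.2. In the same edit, state whether McNemar's test is exact, continuity-corrected or uncorrected.

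Naming and justifying a direction for each marker would also cure the defect. It would need to be done without knowledge of the marker results, and SAP 7.6 records that an interim analysis has already been run without saying whether it covered them. The two-sided rule avoids that question.

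The cost is one or two sentences, with no effect on sample size, data collection or the primary analysis.
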